#### **8.2.4 RETENTION OF SAMPLES FOR VIRAL SAFETY AND ANY FUTURE VIRAL TESTING**

In compliance with the “*Guideline on the clinical investigation of human normal immunoglobulin for intravenous administration (IVIg)*” (EMA/CHMP/BPWP/94033/2007 rev.3), a serum sample before treatment at the screening visit and a serum sample at the study termination visit CCI must be drawn from each patient and stored for at least 2 years, following study closure (last patient last visit), at  $\leq -70^{\circ}\text{C}$  temperature for viral safety and any future viral testing at the central laboratory. At the end of that period, the samples should be destroyed.

#### **8.2.5 ADVERSE EVENT**

All serious and non-serious AEs, will be collected for all study periods, evaluated with regard to the infusion rate, and recorded as indicated in the Section 9, Safety Reporting Rules.

In particular, infusion AEs will be collected, defined as AEs occurring during or within 1 hour, 24 hours, and 72 hours following each infusion.

Severity and causality correlation to the therapy will be evaluated. Definition and reporting for event and collection of AEs are described in Section 9, Safety Reporting Rules.

Note that any potential undesirable effect from screening to infusion 1 will be reported as medical history. Those effects considered serious and related to prior IVIg, will also be notified to the marketing authorization holder.

### Medical Events of Interest

For this study, the following will be considered medical events of interest (see Section 7.1.2):

- Thrombotic events
- Hemolysis
- Transfusion-related acute lung injury (see Section 7.1.1, Method of Administration)
- Aseptic meningitis
- Acute renal failure
- Neutropenia
- Hypersensitivity reactions (including anaphylaxis)

Anaphylaxis, defined according to NIAID/FAAN clinical criteria (Shaker MS, 2020), is highly likely when any one (1) of the following three (3) criteria are fulfilled:

1. Acute onset of an illness (minutes to several hours) with involvement of the skin, mucosal tissue, or both (eg generalized hives, pruritus or flushing, swollen lips-tongue-uvula)  
AND AT LEAST 1 OF THE FOLLOWING:
  - a. Respiratory compromise (eg dyspnea, wheeze-bronchospasm, stridor, reduced peak expiratory flow (PEF), hypoxemia)
  - b. Reduced Blood Pressure (BP) or associated symptoms (eg hypotonia [collapse], syncope, incontinence)
2. Two or more of the following that occur rapidly after the exposure to a likely allergen for that patient (minutes to several hours):
  - a. Involvement of the skin-mucosal tissue (eg generalized hives, itch-flush, swollen lips-tongue-uvula)
  - b. Respiratory compromise (eg dyspnea, wheeze-bronchospasm, stridor, reduced peak expiratory flow (PEF), hypoxemia)
  - c. Reduced Blood Pressure (BP) or associated symptoms (eg hypotonia [collapse], syncope, incontinence)
  - d. Persistent gastrointestinal symptoms (eg crampy abdominal pain,

- vomiting)
3. Reduced BP after exposure to known allergen for that patient (minutes to several hours):
    - a. Infants and children: low systolic BP (age specific) or greater than 30% decrease in systolic BP
    - b. Adults: systolic BP of less than 90 mm Hg or greater than 30% decrease from that person's baseline

### 8.3 DEMOGRAPHIC ASSESSMENT

#### 8.3.1 MEDICAL HISTORY AND DEMOGRAPHIC INFORMATION

The following demographic information, including date of birth, gender and ethnicity, and a complete medical history, will be collected at the screening visit and recorded directly in the eCRF:

- infections history;
- tolerance of previous IgG treatment;
- antibody response to pneumococcal vaccination (when available);
- documented last 3 commercially available IVIg infusions before the study entry;
- baseline IgG levels;
- 2 documented IgG trough levels of  $\geq 6$  g/L within 12 months (1 being within 6 months) prior to enrollment.

In particular, history results relevant to the confirmation of PID diagnosis must be collected. Patients must have a documented history of stable commercially available IVIg therapy at approximately 21- or 28-day intervals for at least 3 infusion cycles prior to receiving Klg10. There must also be documentation of at least 2 trough serum levels of  $\geq 6$  g/L during the previous 6 and 12 months.

#### 8.3.2 CONCOMITANT MEDICATIONS

All medications, drugs and blood products taken or received by the patient starting on the day of the first Klg10 infusion until the study termination visit are to be collected into the e-CRF (see Section 7.5, Concomitant Medications).

#### 8.3.3 CHEST X-RAY

A chest x-ray will be performed at the screening visit if a chest x-ray is not available within last 6 months prior to the ICF signature.

## 8.4 PHARMACOKINETIC ASSESSMENT (PK EVALUATION SET)

Pharmacokinetic assessments will be performed in approximately 24 adult patients in order to have 20 evaluable patients before and after the 5th study infusion (28-day infusion schedule) or the 7th study infusion (21-day treatment schedule), when steady state is expected to be achieved (after 5 half-lives of regular infusion of the IMP). Interim PK analysis will be performed when approximately 24 adult patients (20 evaluable patients) complete intense PK sampling before and after infusion 5 for the 28-day schedule or infusion 7 for 21-day schedule.

Blood samples (approximately 20 mL) will be obtained at the following time-points:

- 30 minutes to 10 minutes pre-infusion
- 30 minutes ( $\pm$  5 minutes) post-infusion
- 2 hours ( $\pm$  15 minutes) post-infusion
- 24 hours ( $\pm$  2 hours) post-infusion
- 72 hours ( $\pm$  2 hours) post-infusion
- 7 days ( $\pm$  1 day) post-infusion
- 14 days ( $\pm$  1 day) post-infusion
- 21 days ( $\pm$  1 day) post-infusion
- 28 days ( $\pm$  2 days) post-infusion (only for 28 days treatment schedule)

Information about the PK assessment will be recorded in the source documentation at the study site and in the eCRF.

### 8.4.1 PK PARAMETERS OF TOTAL IgG

Blood samples for the analysis of PK parameters for total IgG will be taken before and after infusion 5 for the 28-day infusion schedule or infusion 7 for the 21-day infusion schedule, and at the time points indicated above in Section 8.4, Pharmacokinetic Assessment.

Total IgG levels and the following PK parameters will be evaluated. The PK parameters are also described in Section 10.4.4.

Plasma concentration-time curve, half-life,  $AUC_{0-t}$ ,  $AUC_{0-inf}$ , volume of distribution,  $C_{max}$ ,  $T_{max}$ , and elimination rate constant.  $AUC_{0-inf}$  will be evaluated if data meet PK acceptance criteria to elimination parameters; AUC over dosing interval (21-day or 28-day) ( $AUC_{tau}$ ) and other parameters may be derived.

Data about the above total IgG levels will be recorded in the source documentation at the study site and in the eCRF.

#### **8.4.2 IgG SUBCLASSES LEVELS**

Blood samples for the analysis of IgG subclasses levels (IgG1, IgG2, IgG3, IgG4) will be taken before (as for all patients) and after the infusion 5 (28-day infusion schedule) or infusion 7 (21-day infusion schedule) at the time points indicated above in Section 8.4, Pharmacokinetic Assessment.

IgG subclasses levels will be recorded in the source documentation at the study site and in the eCRF.

#### **8.4.3 PK PARAMETERS OF SPECIFIC IgG ANTIBODIES**

Blood samples for the analysis of PK parameters for specific IgG antibodies (anti-Haemophilus influenza type b, anti-pneumococcal capsular polysaccharide, and anti-Tetanus toxoid) will be taken before and after the infusion 5 (28-day infusion schedule or infusion 7 (21-day infusion schedule) at the time-points indicated in Section 8.4, Pharmacokinetic Assessment.

Specific antibodies levels and the following PK parameters will be evaluated. The PK endpoints are also described in Section 10.4.4.

Plasma concentration-time curve, half-life,  $AUC_{0-t}$ , volume of distribution,  $C_{max}$ ,  $T_{max}$ , and elimination rate constant.  $AUC_{0-inf}$  will be evaluated if data meet PK acceptance criteria to elimination parameters; AUC over dosing interval (21-day or 28-day) ( $AUC_{tau}$ ) and other parameters may be derived.

Data about the above specific IgG antibodies will be recorded in the source documentation at the study site and in the eCRF.

## 9. SAFETY REPORTING RULES

### 9.1 DEFINITIONS

#### 9.1.1 ADVERSE EVENT/ADVERSE DRUG REACTION

An AE is “any untoward medical occurrence in a patient or clinical trial patient administered a medicinal product and which does not necessarily have a causal relationship with this treatment” Directive 2001/20/EC.

An AE can therefore be any unfavourable and unintended sign (including an abnormal laboratory finding), symptom or disease temporally associated with the use of a medicinal (investigational) product, whether or not related to the medicinal (investigational) product.

An ADR is “any untoward and unintended responses to an IMP related to any dose administered.” The definition of ADR covers also medication errors and uses outside what is foreseen in the protocol, including misuse and abuse of the product. The definition implies a reasonable possibility of a causal relationship between the event and Klg10. This means that there are facts (evidence) or arguments to suggest a causal relationship.

#### 9.1.2 SERIOUS ADVERSE EVENTS

A SAE is “any AE that, at any dose:

- results in death,
- is life threatening,
- requires hospitalization or prolongation of existing hospitalization,
- results in persistent or significant disability or incapacity,
- is a congenital anomaly or birth defect.”

These characteristics/consequences have to be considered at the time of the event. For example, regarding a life-threatening event, this refers to an event in which the patient was at risk of death at the time of the event; it does not refer to an event, which hypothetically might have caused death if it was more severe.

Some medical events may jeopardise the patient or may require an intervention to prevent one of the above characteristics/consequences. Such events (hereinafter referred to as ‘important medical events’) should also be considered as ‘serious’ in accordance with the definition.

A **non-serious AE** is an AE that does not meet the above criteria.

### 9.1.3 UNEXPECTED ADVERSE DRUG REACTIONS

An unexpected adverse reaction is an “adverse reaction, the nature or severity of which is not consistent with the applicable product information (e.g., Investigator’s brochure for an unauthorized investigational product or summary of product characteristics for an authorized product).”

Reports which add significant information on the specificity, increase of occurrence, or severity of a known, already documented serious adverse reaction constitute unexpected events.

### 9.1.4 CAUSALITY CORRELATION

The Investigator should evaluate the association between the AE and the on-going treatment using information found in the Investigator’s Brochure in conjunction with the patient’s pre-existing medical conditions and concomitant medications and the timing of the AE relative to the administration of Klg10. Any AE will be reported as “Related” or “Not Related” to Klg10 in accordance with the following definitions, elaborated from those of the World Health Organization:

#### Related:

**Any event which falls into one of the below definitions (certain, probable or possible), it should be considered as “Related” to study drug.**

#### Certainly Related

A clinical event (including laboratory test abnormalities):

- occurring in a plausible time relationship to drug administration;
- which cannot be explained by concurrent disease or other drugs;
- which response to withdrawal of the drug (de-challenge) is clinically plausible;
- which must be definitively associated pharmacologically or phenomenologically, using a satisfactory “re-challenge” procedure, if necessary.

Probably related:

A clinical event (including laboratory test abnormalities):

- with reasonable time sequence to administration of the drug;
- unlikely to be attributed to concurrent disease or other drugs or chemicals;
- which follows a clinically reasonable response on withdrawal (de-challenge);
- “re-challenge” information is not required to fulfil this definition.

Possibly related:

A clinical event (including laboratory test abnormalities):

- with a reasonable time sequence to administration of the drug;
- which could also be explained by concurrent disease or other drugs or chemicals;
- information on drug withdrawal may be lacking or unclear.

Not related:

An event for which sufficient information exists to conclude that the etiology of the event is unrelated to Klg10.

Please note that this definition is intended to be used when the exclusion of drug causality of a clinical event is supported by the existence of an alternative cause (e.g., concomitant medications, medical history, concomitant diseases, disease under study, or other) which should be clearly specified with additional details.

If a possible correlation cannot be excluded, the definition to be used is “Related.”

## 9.2 REPORTING METHODS

**Any serious and non-serious AE** must be communicated to Kedrion or its designee. An eCRF will be used for this study. All serious AEs will be communicated to Kedrion/designee as noted in Section 9.2.1.

### 9.2.1 SERIOUS ADVERSE EVENT/SERIOUS ADVERSE DRUG REACTIONS

All SAEs/serious adverse drug reactions (SADRs) must be reported by the Investigator to the Sponsor or its designee by entering all information relevant to the event in the appropriate "Serious Adverse Event(SAE)/Medical Event of Interest Report Form" **immediately** and, in any case, **no later than 24 hours** following the receipt of this information. A detailed report (**follow-up**) on the case should be supplied by the Investigator within the **subsequent 3 calendar days**, using the same form.

In the case of a SAE with a **fatal** outcome, the Investigator must notify not only the Sponsor/designee but also the local IEC/IRB and must provide any additional required information.

### 9.2.2 NON-SERIOUS ADVERSE EVENTS

The Investigator is required to notify the Sponsor/designee of all non-serious AEs. This information should be reported by the Investigator to the Sponsor/designee by updating the eCRF "Adverse Event Report Form" following the receipt of this information.

### 9.2.3 ABNORMALITIES IN LABORATORY PARAMETERS

The Investigator must evaluate the clinical significance of all abnormal laboratory values based on standard laboratory reference values. Any clinically significant abnormality must be fully investigated. The term "clinically significant" refers to any abnormal value that, according to the Investigator, represents an important clinical problem that requires the intervention of a physician or that otherwise may fall within the definition of a "serious" AE. When clinical significance is indicated, further analysis or other assessments must be obtained in order to determine the significance or cause of an abnormal result, or to monitor the course of an AE. Any persistently abnormal value must be monitored at the Investigator's discretion. Clinically significant abnormal results shall be documented in the appropriate eCRF.

Pregnancy test will be performed locally at each site. Hematology, chemistry, urinalysis, IgG levels, subclasses, specific antibodies, and intravascular hemolysis testing will be analyzed centrally. Direct Coombs and urine hemosiderin can be tested either centrally or at site level. For centralized tests, Investigators will receive the results and the reference normal ranges for patient monitoring.

#### **9.2.4 PRE-EXISTING AND CONCOMITANT DISEASES**

Pre-existing diseases that are present prior to the study entry before the ICF signature up to the first Klg10 infusion must be reported in the appropriate eCRF (Medical History). Please note that signs/symptoms of a pre-existing disease that occur with the same severity, frequency or duration after the administration of Klg10 will be considered as Medical History.

Concomitant diseases that occur following the first Klg10 infusion until the study termination visit or cases that show an increase in the severity or the duration of a pre-existing disease must be reported as AEs.

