The largest group of patients with antibody deficiency are classified as common variable immunodeficiency (CVID) with an estimated prevalence of 1 in 50,000. Diagnosis of CVID is based on the exclusion of other known causes of humoral immune defects (Resnick ES, 2012). It is defined principally as low IgG (often with low IgA) together with a significant impairment of specific antibody production in response to bacterial vaccine or natural infectious challenge (Conley ME, 1999; Cunningham-Rundles C, 1999). Males and females are equally affected, and presentation is most common at the ages of 20 to 40 with only about 20% of patients diagnosed in childhood. While some genetic defects have been shown to cause CVID, in most patients the molecular defect remains unknown. Signs and symptoms of CVID are generally that of recurrent pyogenic sino-pulmonary infections. The patients are also prone to infection with enteric pathogens, such as *Giardia lamblia* infection, and a variety of autoimmune disorders (Resnick ES, 2012). A number of studies have demonstrated the steadily decreasing incidence of infection with increasing frequency of IVIg administration in CVID patients.

In PID diseases with primary antibody deficiency and bacterial infections, lifelong replacement therapy with IgG is required and necessary to reduce incidence (frequency) and severity of infections and prevent long-term deterioration principally in pulmonary functions. Treatment recommendation is that patients with primary antibody deficiency should be treated with IVIg at a starting dose of 400-600 mg/kg every 3 to 4 weeks (Jolles S, 2015). Less frequent treatment, or use of lower doses, is not substantiated by clinical data. Each patient may demonstrate his or her own individual response to therapy, and experience dramatic differences in the frequency and severity of infections with moderate changes in the dose of IVIg (Shapiro RS, 2017). Patients suffering from a serious acute infection often benefit from booster doses of IVIg. Ultimately, IVIg dosage must be individualized based upon the response of the patient (frequency of infection episodes) and potential serious complication of the primary disease (e.g., bronchiectases).

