After all screening procedures have been conducted and reviewed by the site principal investigator, the patient's eligibility assessment will be carried out by the CRO's Medical Monitor, who will consult the study principal investigator for confirmation as needed, based on key protocol inclusion and exclusion criteria to promote appropriate patient enrollment and data quality. Sites should submit specific Screening information as soon as possible after the Screening Visit, but only when all required information is available, for review by the Medical Monitor prior to proceeding to the Baseline visit. Patients who are deemed eligible by the Medical Monitor will be allowed to proceed in the study.

Initially the trial will include adult PID patients and adolescents in whom data will be collected. The data of at least 10 patients with at least 3 infusions (i.e., 3 months of exposure) will be reviewed by a Data Safety Monitoring Board (DSMB), and after positive evaluation, Kedrion intends to continue studying the efficacy and safety of Klg10 in the young age group of PID patients (children < 12 years of age).

There is no risk to the patient in completing QoL questionnaires and self-reported health care utilization. Completion of questionnaires and reporting of data could be beneficial in determining the continuous utilization of IVIg in the treatment of PID.

The selected study centers are highly specialized centers with previous experience in the treatment of PID patients with IVIg as well as with experience in clinical trials. Patients will have diaries, and local medical staff will contact them to check on their well-being when they

are not at a regular site-scheduled visit. All patients will have the first infusion of IgG at a lower infusion speed which may be gradually increased based on individual experience and tolerance. Higher infusion speed might play an important role in determining the safety profile of the product (Cherin P, 2016).

The following adverse reactions are known occasionally to be associated with IVIg products: chills, headache (which is the most frequent AE described in previous clinical trials with IVIg in PID patients, range 22-52% of patients) (Schroeder HW, 2012), dizziness, fever, vomiting, allergic reactions, nausea, arthralgia, low blood pressure, and moderate low back pain.

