#### 10.1.2. AE related

The following information will be summarized overall and by infusion schedule:

- Number and proportion of Klg10 infusions for which the infusion rate is decreased due to AEs (from infusion 1 to infusion 17)
- Number and proportion of Klg10 infusions with 1 or more infusional (temporally-associated) AE (from infusion 1 to infusion 17).
- A 1-sided 95% confidence interval (CI) will be produced for the proportion of infusions with 1 or more temporally-associated AEs (including AEs determined not to be product-related) using an exact binomial method. Due to the clustered nature of the data, a Design Effect will be applied to the confidence interval. An analysis of variance method will be used to calculate the Intra Cluster Correlation Coefficient (5).

For this analysis, safety will be declared if the upper 1-sided 95% confidence is less than 0.4 (counting overall infusions).

This document is confidential.

For producing such CI the following steps will be performed:

**1 Calculate the raw 1-sided 95% CI:** This will be done using an exact binomial method (e.g. Clopper Pearson)

**2 Calculate the intraclass correlation coefficient:** The point estimate via ANOVA method is given by Wu (5) as:

$$\widehat{\rho}_A = \frac{MSB - MSW}{MSB + (n_A - 1) * MSW}$$

where

$$n_A = \frac{1}{(k - 1)} \left( N - \frac{\sum n_i^2}{N} \right)$$

$$MSB = \frac{1}{(k - 1)} \left( \sum \frac{Z_i^2}{n_i} - \frac{(\sum Z_i)^2}{N} \right)$$

$$MSW = \frac{1}{(N - k)} \left( \sum Z_i - \sum \frac{Z_i^2}{n_i} \right)$$

and

MSB and MSW: between-group and within-group mean squares from a one-way analysis of variance of the binary data

k: number of clusters (patients)

ni : number of observations (infusions) on the ith cluster (patient)

Yij: the response of patient j in cluster i (with Yij: 0 meaning negative to the event of interest and Yij: 1 meaning positive to the event of interest where the event of interest having at least one associated infusional Adverse Event). The sum Yij is equal to the number of successes on the ith cluster and it is labelled as Zi i.e.

$$Z_i = \sum_j Y_{ij}$$

N is the number of total observations (infusions) in the considered analysis i.e.

$$N = \sum n_i$$

**3 Calculate the Design Effect:** A conservative approach is given by Eldridge (6). The Design effect can be written as:

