## 10.3. Adverse Events / Adverse Drug Reactions

Adverse events (AEs) will be coded using MedDRA to give a PT and a SOC term for each event. At the end of the study, AEs will be recoded applying the latest available MedDRA version available at this time point.

Adverse events temporally associated with the infusion are AEs occurring during infusion or within 72 hours after the end of infusion and are defined as infusional AEs.

Summary tables will be based on treatment-emergent adverse events (TEAEs), defined as those events with onset date/time at or after the first Klg10 infusion until the patient's last study visit.

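### The two sentences of Protocol 9.2.4 conflict, so a pre-existing symptom that worsens in one respect meets both rules and one that only becomes more frequent is never an AE; both can drop out of the infusional-AE proportion tested against 0.4

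*Protocol*

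**What the plan says.** Protocol 9.2.4 has two rules for what happens after the first infusion.

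- History rule: "signs/symptoms of a pre-existing disease that occur with the same severity, frequency or duration" once KIg10 has been given count as Medical History.
- AE rule: new concomitant diseases are AEs, and "cases that show an increase in the severity or the duration of a pre-existing disease must be reported as AEs". Frequency is not listed here.

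Protocol 9.1.1 defines an AE broadly. It includes any sign, "symptom or disease temporally associated with the use of a medicinal (investigational) product, whether or not related to the medicinal (investigational) product".

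SAP 10.3 takes the temporally associated events from the AE data: they are "AEs occurring during infusion or within 72 hours after the end of infusion and are defined as infusional AEs". SAP 10.1.2 then sets a one-sided 95% confidence interval "for the proportion of infusions with 1 or more temporally-associated AEs (including AEs determined not to be product-related") and declares safety if the upper limit is below 0.4. Protocol 10.4.3 states the same criterion. Neither document has a rule that brings a Medical History entry back into this count.

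**The concern.** The tested proportion deliberately counts AEs whatever their cause, so a view that an event is not due to KIg10 should not remove it. Section 9.2.4 allows a similar judgement, that this is only the old complaint, to be made before the event becomes an AE at all.

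Overlap with pre-existing complaints is plausible. All patients are already on IVIg, and tolerance of previous IgG is collected as medical history (Protocol 4.4.1, 6.2). Protocol 2.3 lists "headache (which is the most frequent AE described in previous clinical trials with IVIg in PID patients, range 22-52% of patients"), and exclusion criterion 15 removes only migraine that medication does not completely control. A patient whose pre-existing headache keeps its usual severity and length but now returns after infusions fits the history rule and not the AE rule.

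At stake is a formal pass/fail safety statement. The undercount would also depend on the site, because some sites will read the conditions as alternatives and others as cumulative.

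**Working it through.** **The two rules side by side.** Let each of severity, frequency and duration be unchanged or increased, which gives eight patterns. Read the first rule literally (one match is enough) and the second as written (increase in severity or duration).

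| Pattern | History rule met? | AE rule met? |
|---|---|---|
| All three unchanged | yes | no |
| Frequency alone increased | yes | no |
| Severity and/or duration increased, at least one of the three unchanged (5 patterns) | yes | yes |
| All three increased | no | yes |

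Only the first and last rows are clean. Five patterns meet both rules. The frequency-only pattern is always history. If a site reads the first rule as requiring all three to match, frequency-only meets neither rule and falls back on 9.1.1, where it would be an AE. The same event is then recorded differently at different sites.

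**Effect on the 0.4 criterion.** The plan gives no sample size or power for this test, so there is no figure of its own to reproduce. The stated 90% power for 40 patients belongs to the serious-infection endpoint.

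Inputs from the documents:
- 13 infusions per patient (28-day schedule) or 17 (21-day schedule), from the Time and Events tables.
- About 50 patients (Protocol 5). The illustration uses N = 50 × 13 = 650.
- Reported limit = design effect × exact binomial upper limit (SAP 10.1.2, step 4), applied as written.

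Assumptions:
- The true proportion p.
- The ICC.
- u, the share of AE-positive infusions whose only temporally associated AE is filed as history.
- Equal cluster sizes, so the SAP's design effect reduces to DE = 1 + (m − 1) × ICC with m = 13.

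The exact limit is U(x) = the 0.95 quantile of Beta(x + 1, N − x). The test passes if DE × U(x) < 0.4.

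ICC 0 (DE 1):
- Largest passing count: 239, and 239/650 = 36.8%.
- p = 40%: x = 260, U = 0.433, fail. With u = 10%, x = 234, U = 0.392, pass. The switch needs u of at least 1 − 239/260 = 8.1%.
- p = 38%: x = 247, U = 0.412, fail. With u = 5%, x = 235, U = 0.394, pass.
- p = 35%: x = 227, U = 0.381. It passes without any reclassification.

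ICC 0.05 (DE = 1 + 12 × 0.05 = 1.6):
- U must be below 0.4/1.6 = 0.25. Largest passing count: 143, and 143/650 = 22.0%.
- p = 25% passes only if u is at least 1 − 0.22/0.25 = 12.0%. p = 20% passes anyway. p = 40% would need u of at least 45.0%.

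ICC 0.1 (DE = 2.2): the cut-off is 101/650 = 15.5%, and p = 20% needs u of at least 22.3%.

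The ICC-0 cut-off varies little with size: 36.3% for 40 × 13, 36.8% for 40 × 17 and 37.2% for 50 × 17 infusions.

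**The case against.** The best defence is that keeping an unchanged baseline symptom out of the AE counts is ordinary practice. That stands. A reader might infer that 9.2.4 as a whole removes real on-treatment events; the documents do not show this. The fault lies in the alternatives in the first sentence and the missing frequency in the second.

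The defence can also point to text that pulls towards reporting: the broad definition in 9.1.1, the instruction in 9.1.4 to call an event related if a link cannot be excluded, and the diary's emphasis on the first 24 and 72 hours (4.4.2). The rule is also limited to signs and symptoms of a pre-existing disease. These points reduce the likely number of misfiled events. None of them says which sentence of 9.2.4 prevails.

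Two stronger readings are tempting and should not be taken.

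- Infections. Protocol 2.1 says "Signs and symptoms of CVID are generally that of recurrent pyogenic sino-pulmonary infections", so one might infer that infections can be filed as history too. That sentence is background. Sections 6.6, 6.7 and 6.10 require any infections to be recorded with the AEs, 8.1.1 requires all acute serious bacterial infections in the eCRF, and 8.1.5 gives other infections their own eCRF pages.
- Point estimates. A true 42% with 10% reclassified is recorded as 0.42 × 0.9 = 0.378, which looks like a crossing of 0.4. The SAP tests the limit: 246/650 gives 0.411 at ICC 0 and still fails. At ICC 0.02 (DE 1.24) the cut-off is 189/650 = 29.1%, and even 30% reclassified (0.42 × 0.7 = 29.4%) fails.

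**Conclusion.** The wording defect is real, and no other section resolves it. Events that worsened in one respect, or only became more frequent, can be left out of the AE counts and of the infusional-AE numerator. The numerator can only fall, which favours declaring safety.

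Whether this would change the declared result is not known. In the illustration, a reclassified share of about 5 to 12% matters only when the true proportion lies just above the pass limit: about 37 to 40% at ICC 0, or about 22 to 25% at ICC 0.05. Elsewhere the decision stays the same. These figures rest on assumed values of p, u and ICC, on equal cluster sizes, and on an ICC held fixed although it would be re-estimated from the recorded data. Whether the exact limit should be multiplied by the design effect at all is a separate question. The primary serious-infection analysis and its stated power are not affected by this point.

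**What to change.** Protocol 9.2.4:
- A sign or symptom of a pre-existing disease is Medical History only if it is unchanged in severity, in frequency and in duration.
- An increase in any one of the three is an AE.

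SAP 10.1.2: add a sensitivity analysis of the 0.4 criterion that also counts recurrences of pre-existing symptoms recorded with onset during an infusion or within 72 hours after its end. This belongs in a sensitivity analysis and not in the main count. Counting every such onset in the main analysis would turn unchanged intermittent complaints into infusional AEs and could push the proportion up artificially.

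Cost: a wording change, a memo to sites and one extra table. The sensitivity analysis needs an onset date and time for these recurrences, so the eCRF must capture them. SAP 6.6 shows that patients have already been enrolled, so post-infusion Medical History entries made under the present wording should be checked before database lock. The reported AE rate may become slightly less favourable.
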